8.5.2 Efficacy Population

The evaluable population for the primary endpoint of ORR will include all enrolled patients who have measurable disease present at baseline, have received at least one complete cycle of therapy, and have had at least 1 radiographic response assessment or been removed from study due to event of clinical progression. Over-enrollment by approximately 10% is planned to ensure at least 37 patients are evaluable for primary endpoint of ORR.

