1.0 TRIAL SUMMARY

[figure not shown]
Abbreviated Title	Pembrolizumab plus GM-CSF Induction in Advanced Biliary Cancers
Trial Phase	II
Clinical Indication	Advanced biliary cancers including unresectable intrahepatic or extrahepatic cholangiocarcinoma and gall bladder carcinoma
Trial Type	Open label, single arm phase II therapeutic clinical trial
Type of control	None
Route of administration	Intravenous (pembrolizumab) and subcutaneous (GM-CSF)
Trial Blinding	N/A
Treatment Groups	N/A (not randomized)
Number of trial subjects	Total enrollment of 42 subjects for expected PFS6-evaluable n=40 and overall response evaluable n=37, combined between the following three cohorts: Stage 1: n=9 (completed) Stage 2: n=18 (completed) Expansion Cohort: n=15
Estimated enrollment period	Stages 1 and 2: 16 months (completed); Expansion Cohort: 12 months
Estimated duration of trial	52 months for accrual plus up to 2 years on treatment from start of treatment of last enrolled patient in the Expansion Cohort, with potential for up to 2 additional years of survival follow up in event that last patient has prolonged stable disease and discontinues without progression after 24 months or 35 cycles
Duration of Participation	Expect median time on pembrolizumab treatment of 6 months

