8.3 Definition of Study Endpoints

8.3.1 Primary Endpoint

The primary endpoint was amended to be overall response rate (**ORR**) with addition of Expansion Cohort, based upon the promising responses observed during Stages 1 and 2 (Safety and Efficacy Cohorts). **ORR** is defined as the proportion of subjects with RECIST 1.1-measurable disease at study entry who have a complete response (CR) or partial response (PR) (confirmed + unconfirmed) using RECIST 1.1¹ at any time during the main study. Measurable disease has been added as a required inclusion criterion for Expansion Cohort eligibility. Re-induction and Second Course ORR (rORR, sORR) will be determined based upon response after first dose of re-induction or first dose of Second Course. Subjects with measurable disease at study entry who have unknown or missing response information will be treated as non-responders. Subjects with non-measurable disease at study entry will be excluded from ORR and DOR analyses.

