8.4 Sample Size and Accrual Rate

8.4.1 Sample Size

For the primary endpoint of ORR, a sample size of 37 response-evaluable subjects will provide power of 77% with 2-sided 5% alpha and 88% with 1-sided 5% alpha to show ORR improvement from H_0 of 5% to H_1 of 20%, under protocol treatment. Based upon a subset with non-measurable disease enrolled to Stages 1 and 2 before amendment requiring RECIST 1.1-measurable tumors for enrollment to Expansion Cohort, along with potential for dropout in this population with comorbidity of biliary obstruction and liver disease, it is estimated that total enrollment of 42 subjects will include at least 37 response-evaluable subjects.

The key secondary endpoint of %PFS6 was previously the primary endpoint for Stages 1 and 2, prior to amendment adding Expansion Cohort, which also changed to primary endpoint of ORR based upon the promising response rate observed in Stages 1 and 2. For the key secondary endpoint of PFS, an expected overall study PFS-evaluable sample size of at least 40 patients will have power 78% with 2-sided alpha 5% and power 87% with 1-sided alpha to show PFS improvement from H_0 of 20% to H_1 of 40% on protocol therapy.

Pre-amendment, a Simon's 2 stage design was employed to determine if adequate efficacy was observed in Stage 1 to warrant proceeding to Stage 2. The pembrolizumab/GM-CSF combination was considered worthy of additional investigation if the true %PFS6 is 50%, and hence the alternative hypothesis, $\%PFS_1=0.50$. Therefore assuming an α error probability of 5%, and a β error of 20%, the first stage had 9 patients. If ≤ 2 of 9 had been observed progression-free, the study would not proceed to second stage. Since ≥ 3 of 9 patients are observed progression-free at 6 months (4/9 achieved PFS6 in Stage 1), enrollment continued to the second stage with 18 additional patients, with a goal of at least 24 evaluable patients (with planned over-enrollment of 3 additional patients to account for expected 10% dropout rate). If ≤ 9 patients are observed progression-free at 6 months out of 24 evaluable patients by the end of second stage, then no further investigation of the drug is warranted under this PFS6 hypothesis. Conversely, if ≥ 10 patients are progression-free at 6 months among Stages 1 and 2 subjects, the study would be considered positive for the hypothesis: H_0 : $\%PFS_0 < 25\%$ versus H_a : $\%PFS_1 > 50\%$.

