8.6 Planned Analyses

8.6.1 Primary Endpoint Analysis

With expectation of at least 37 subjects with RECIST 1.1-measurable disease evaluable for response, ORR calculated as the proportion with CR + PR (confirmed + unconfirmed) by RECIST 1.1 at any time during the main study. Subjects with measurable disease at study entry who have unknown or missing response information will be treated as non-responders. Subjects with non-measurable disease at study entry will be excluded from ORR and DOR analyses.

For the primary endpoint of ORR, a sample size of 37 response-evaluable subjects will provide power of 77% with 2-sided 5% alpha and 88% with 1-sided 5% alpha to show ORR improvement from H_0 of 5% to H_1 of 20% on protocol treatment, using Fisher's Exact tests. Based upon a subset with non-measurable disease enrolled to Stages 1 and 2 before amendment requiring RECIST 1.1-measurable tumors for study enrollment to Expansion Cohort, along with potential for dropout in this population with comorbidity of biliary obstruction and liver disease, it is estimated that total enrollment of 42 subjects will yield approximately 37 response-evaluable subjects.

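### The primary ORR has two unreconciled denominators, and the narrower one (8.5.2) generally biases ORR upward by a modest amount

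*Combined protocol and SAP*

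**What the plan says.** Section 8.3.1 defines ORR over subjects with RECIST 1.1-measurable disease at entry and adds: "Subjects with measurable disease at study entry who have unknown or missing response information will be treated as non-responders". Section 8.6.1, the primary analysis section, repeats that rule and names a single exclusion: "Subjects with non-measurable disease at study entry will be excluded from ORR and DOR analyses".

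Section 8.5.2 defines the evaluable population for the same endpoint. Besides measurable disease at baseline, patients must "have received at least one complete cycle of therapy, and have had at least 1 radiographic response assessment or been removed from study" because of clinical progression. It continues: "Over-enrollment by approximately 10% is planned to ensure at least 37 patients are evaluable for primary endpoint of ORR".

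Other text mixes the two. Section 8.6.1 opens "With expectation of at least 37 subjects with RECIST 1.1-measurable disease evaluable for response". Section 8.4.1 explains the step from 42 enrolled to 37 evaluable by two causes: "Based upon a subset with non-measurable disease enrolled to Stages 1 and 2 before amendment", and "along with potential for dropout in this population with comorbidity of biliary obstruction and liver disease". The Trial Summary gives "Total enrollment of 42 subjects for expected PFS6-evaluable n=40 and overall response evaluable n=37".

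**The concern.** Take a patient with measurable disease who stops during cycle 1 and is never scanned, or who withdraws, is lost, dies without recorded clinical progression, or moves to new therapy or hospice before any response scan. Sections 8.3.1 and 8.6.1 count this patient as a non-responder. Section 8.5.2 leaves the patient out.

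Under 8.5.2, entry to the primary set therefore depends on what happens after treatment starts. A response needs a scan, so every patient dropped for lack of one is a non-responder: the denominator shrinks and the numerator does not. The word *generally* is needed because a patient with an incomplete first cycle who is scanned later and responds would leave both.

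The first on-treatment scan is due at 8 weeks, and section 4.3.6.2 puts historical median PFS at about 2 to 3 months, so early losses are plausible. Some may still be kept: section 7.1.6.3.1 allows efficacy assessments at the Safety Follow-Up Visit, section 7.1.6.4 continues imaging after discontinuation without progression, and a hospice transfer may be recorded as clinical progression. The trial is open-label and response is assessed locally, so the denominator should not be left to be chosen after the data are seen.

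**Working it through.** **Inputs.** Null ORR 5%, alternative 20%, 37 response-evaluable, stated power 77% (two-sided 5%) and 88% (one-sided 5%): sections 8.4.1 and 8.6.1. Enrollment of 42: Trial Summary. Let k be the number of measurable patients that 8.5.2 drops. The plan does not give k. At least one of the 42 had non-measurable disease (8.4.1), so at most 41 are measurable, and with 37 evaluable k is at most 41 − 37 = 4. The range used is k = 1 to 4.

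**Reproducing the plan's power.** The exact one-sample binomial with n = 37 gives:

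- at least 5 responders: P = 0.0359 at 5%, power 0.888 at 20% (plan 88%)
- at least 6 responders: P = 0.0095 at 5%, power 0.7775 at 20% (plan 77%)

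Both stated figures are reproduced.

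**Boundary by denominator**, upper tail at a true ORR of 5%:

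| n | P(X ≥ 5) | P(X ≥ 6) |
|---|---|---|
| 37 | 0.0359 | 0.0095 |
| 38 | 0.0397 | 0.0109 |
| 39 | 0.0438 | 0.0123 |
| 40 | 0.0480 | 0.0139 |
| 41 | 0.0525 | 0.0156 |
| 42 | 0.0573 | 0.0174 |

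With an upper tail of at most 0.025 the boundary is 6 for every n from 37 to 42. With at most 0.05 it is 5 for n = 37 to 40 and 6 for n = 41 and 42.

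**Size of the bias.** Assume that the dropped patients cannot respond.

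- An ORR of 20% on 37 evaluable corresponds to 0.20 × 37/(37 + k) on all measurable patients.
- If the true ORR is 5% in all 37 + k, the rate in the 37 is 0.05 × (37 + k)/37. The true error of the rule is the binomial tail at that rate.

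| k | ORR on all measurable | True error of ≥ 5/37 |
|---|---|---|
| 0 | 20.0% | 3.6% |
| 1 | 19.5% | 4.0% |
| 2 | 19.0% | 4.35% |
| 3 | 18.5% | 4.8% |
| 4 | 18.0% | 5.2% |

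The upper-tail error of ≥ 6/37 is at most 1.5%, at k = 4.

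**A plausible k.** The Trial Summary expects 40 PFS6-evaluable and 37 response-evaluable of 42. If the 42 − 40 = 2 are dropouts and the remaining 40 − 37 = 3 are non-measurable, k is about 2. This split is an assumption.

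**When a decision changes.** No two-sided decision changes, because the boundary is 6 throughout. A one-sided decision changes only with exactly 5 responders, at most 40 evaluable and at least 41 measurable: for example 5/40 (p = 0.048) against 5/41 (p = 0.0525), where k = 1 is enough. That needs at most one non-measurable patient among 42. The chance of exactly 5 responders in 41 is 3.7% at a true ORR of 5% and 7.8% at 20%.

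**The case against.** The strongest reply is that the sections can be harmonised: 8.3.1 defines the endpoint, 8.5.2 the population, and 8.6.1 the handling of missing data inside it. Section 8.5.2 keeps unscanned patients removed for clinical progression, so the missing-response rule would still have work to do there. The allowance for dropout between 42 and 37 also makes sense only if some measurable patients leave the denominator. Section 5.9 plans about 10% over-enrollment for non-evaluability and sends the reader to 8.6 for the analysis populations. Those now stand in 8.5; the numbering appears to have shifted by one, since section 7.1.4 cites 8.7.3 for correlative analyses now in 8.6.3.

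These points show that 8.5.2 has real support. They do not settle the matter, because nowhere is the missing-response rule limited to the 8.5.2 set, and 8.3.1 applies it to subjects with measurable disease at study entry.

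The objection on size stands. At k = 2 the shift is 1.0 point, and the one-sided error stays below 5% for k = 1 to 3. Two further cautions also stand. Section 8.3.2 counts censored patients without progression in the PFS6 denominator, so the 2 patients not evaluable for PFS6 need not be ordinary dropouts, and the estimate of k is weak. The documents also do not say to which denominator the 5% null refers; the calculation takes it as all measurable patients.

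**Conclusion.** The concern holds. The plan gives two different denominators for its primary endpoint without saying which governs. Following 8.5.2 as written would remove unscanned non-responders whom 8.3.1 and 8.6.1 count; following 8.3.1 and 8.6.1, the bias does not arise. The effect is modest: 0.5 to 2.0 points of ORR at 20%, and a one-sided error that passes 5% only at k = 4. This rests on an assumed k of 1 to 4, 37 evaluable patients and no responders among those dropped. The plan should be corrected because the primary denominator is undefined; a changed conclusion is not likely.

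**What to change.** State that the 8.3.1/8.6.1 definition governs the primary ORR: all treated patients with RECIST 1.1-measurable disease at baseline, with missing or unevaluable response counted as non-response. *Treated* is an added clarification, consistent with PFS and OS, which already start at first dose (section 8.3.2). Align 8.4.1 and 8.5.2 to this. Keep the current 8.5.2 set as a labelled sensitivity analysis, reporting how many measurable patients it drops and why. Apply the exact boundary to the actual n.

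The cost is SAP wording, with no extra data. The headline ORR may fall by up to about 2 points. For n = 38 to 40 the one-sided boundary stays at 5, and power is 88.6% to 88.7% if 20% is the rate in the 37 evaluable patients (rate 0.20 × 37/n), against 88.8% at n = 37. If n reaches 41 the one-sided boundary becomes 6. Power is then 85.6% at an ORR of 20% in all 41, or 77.4% if 20% is the rate in 37 evaluable patients, against the stated 88%.

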8.6 Planned Analyses

8.6.1 Primary Endpoint Analysis

With expectation of at least 37 subjects with RECIST 1.1-measurable disease evaluable for response, ORR calculated as the proportion with CR + PR (confirmed + unconfirmed) by RECIST 1.1 at any time during the main study. Subjects with measurable disease at study entry who have unknown or missing response information will be treated as non-responders. Subjects with non-measurable disease at study entry will be excluded from ORR and DOR analyses.

For the primary endpoint of ORR, a sample size of 37 response-evaluable subjects will provide power of 77% with 2-sided 5% alpha and 88% with 1-sided 5% alpha to show ORR improvement from H_0 of 5% to H_1 of 20% on protocol treatment, using Fisher's Exact tests. Based upon a subset with non-measurable disease enrolled to Stages 1 and 2 before amendment requiring RECIST 1.1-measurable tumors for study enrollment to Expansion Cohort, along with potential for dropout in this population with comorbidity of biliary obstruction and liver disease, it is estimated that total enrollment of 42 subjects will yield approximately 37 response-evaluable subjects.

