8.6.2 Secondary and Exploratory Endpoints

For secondary endpoints, due to the limited sample size in the study, descriptive statistics with mean and 95% confidence intervals will be used. For continuous variables, descriptive statistics will include the number of non-missing values, mean, standard deviation, median, min and maximum. For categorical variables, descriptive statistics will include counts and percentages per category. For comparison between subgroups, ANOVA and t-tests will be used when appropriate to determine the association of the efficacy endpoints and specific biomarkers.

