8.6.2.3 PFS6

Proportion with PFS at 6 months (%PFS6) %PFS6 will be a key secondary endpoint for the overall study. With H_0 %PFS6 of approximately 20% (Section 4.3.6.2) and H_1 %PFS6 of 40% if n=40 are evaluable for PFS6, the power is 78% for 2-sided 5% alpha, or 87% with 1-sided 5% alpha using Fisher's Exact tests.

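### The primary ORR test is misnamed as Fisher's exact, and two alphas are quoted with neither made governing and no responder cut-off

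*Combined protocol and SAP*

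**What the plan says.** Section 1.0 describes the study as "Open label, single arm phase II therapeutic clinical trial" and gives the type of control as none. The null rates are fixed historical values: 5% for ORR (sections 3.1 and 4.3.6.1) and 20% for PFS6 (sections 3.2 and 4.3.6.2).

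For ORR with 37 evaluable patients, sections 8.4.1 and 8.6.1 both quote "power of 77% with 2-sided 5% alpha and 88% with 1-sided 5% alpha". Section 8.6.1 adds "on protocol treatment, using Fisher's Exact tests". For PFS6 with 40 evaluable patients, section 8.6.2.3 says "the power is 78% for 2-sided 5% alpha, or 87% with 1-sided 5% alpha using Fisher's Exact tests", while section 8.6.2 says that for secondary endpoints "descriptive statistics with mean and 95% confidence intervals will be used".

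On the evaluable number, section 8.4.1 says "it is estimated that total enrollment of 42 subjects will include at least 37 response-evaluable subjects" and section 8.5.2 says "Over-enrollment by approximately 10% is planned to ensure at least 37 patients are evaluable for primary endpoint of ORR". Section 8.6.1 expects only approximately 37.

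The one final success count in the plan belongs to the superseded PFS6 design in section 8.4.1. It is negative if 9 or fewer "patients are observed progression-free at 6 months out of 24 evaluable patients by the end of second stage", and positive at 10 or more. ORR has no equivalent.

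**The concern.** Fisher's exact test needs a second group, and here there is none. The sentence in 8.6.1 is the only place where the plan names a test for the primary endpoint, so a statistician following it literally has nothing that can be run.

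Quoting power under two alphas is harmless if one is then made governing. Neither is, and no cut-off is stated, so the plan does not define a positive primary result. When the primary endpoint moved from PFS6 to ORR, a design with an explicit decision rule was replaced by one without. What is at stake is whether a particular responder count would be reported as success or failure.

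**Working it through.** **Inputs.** ORR: N=37, null 5%, alternative 20%, alpha 5% one- or two-sided (8.4.1, 8.6.1). PFS6: N=40, null 20%, alternative 40% (8.6.2.3).

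**Method.** With X ~ Binomial(N, p), success is X ≥ r, where r is the smallest count with P(X ≥ r | null) ≤ 0.05 (one-sided) or ≤ 0.025 (two-sided, equal tails). Power is P(X ≥ r | alternative).

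**Step 1: reproduce the plan's figures.**

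| Endpoint | Rule | r | Upper tail under null | Power | Stated |
|---|---|---|---|---|---|
| ORR, N=37 | 1-sided 5% | 5 | 0.0359 | 88.8% | 88% |
| ORR, N=37 | 2-sided 5%, equal-tail | 6 | 0.0095 | 77.8% | 77% |
| PFS6, N=40 | 1-sided 5% | 13 | 0.0432 | 87.1% | 87% |
| PFS6, N=40 | 2-sided 5%, equal-tail | 14 | 0.0194 | 78.9% | 78% |

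All four agree to within one percentage point. A genuine two-sample Fisher test with 37 per arm, 5% against 20%, would have power 36.2% two-sided and 48.8% one-sided. With 40 per arm, 20% against 40%, it would be 40.8% and 53.8%. The plan's figures are therefore one-sample exact binomial figures.

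**Step 2: where the two ORR rules part.** The evaluable N may differ from 37, so the cut-offs are needed over a range.

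| N | P(X≥5), ORR 5% | P(X≥6), ORR 5% | 1-sided r | 2-sided r | P(X=5), ORR 20% |
|---|---|---|---|---|---|
| 33 | 0.0230 | 0.0054 | 5 | 5 | rules agree |
| 34 | 0.0259 | 0.0063 | 5 | 6 | 13.8% |
| 35 | 0.0290 | 0.0073 | 5 | 6 | 12.9% |
| 36 | 0.0324 | 0.0083 | 5 | 6 | 11.9% |
| 37 | 0.0359 | 0.0095 | 5 | 6 | 11.1% |
| 38 | 0.0397 | 0.0109 | 5 | 6 | 10.2% |
| 39 | 0.0438 | 0.0123 | 5 | 6 | 9.3% |
| 40 | 0.0480 | 0.0139 | 5 | 6 | 8.5% |
| 41 | 0.0525 | 0.0156 | 6 | 6 | rules agree |
| 42 | 0.0573 | 0.0174 | 6 | 6 | rules agree |

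From N=29 to 33 both cut-offs are 5. The only disagreement in N=29 to 42 is therefore at exactly 5 responders with N=34 to 40. At N=37 its probability is the difference between the two powers: 0.8880 − 0.7775 = 0.1105.

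**Step 3: the pivotal result.** For 5/37 (13.5%) the one-sided p is 0.036, a success. The equal-tail two-sided p is 2 × 0.0359 = 0.072 and the Clopper-Pearson 95% interval is 4.5% to 28.8%, which contains 5%, a failure. For 6/37 the interval is 6.2% to 32.0%, and both rules succeed.

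**Step 4: the two-sided form matters too.** A minimum-likelihood two-sided exact test adds only outcomes no more probable under the null than the one observed. At N=37, P(X=0) is 0.95^37 = 0.150, well above P(X=5) = 0.026, so no lower-tail outcome is added. The p-value for 5/37 stays at 0.036 and that test rejects, with power 88.8%. The stated 77% fits only the equal-tail form.

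**The case against.** The strongest reply is that nothing of substance is wrong. Fisher's test is named only inside power sentences, it cannot be run without a second sample, and any statistician would use the exact binomial test. The two alphas differ at a single count in a non-randomised phase II trial. Much of this stands: the sample size and powers are sound, the PFS6 wording has no consequence, and the disagreement is narrow. It does not answer the missing decision rule, because 5 of 37 is a realistic result that the plan classifies both ways.

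Three stronger readings are tempting, and the documents do not support them.

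- *The two-sided rule must be imposed because its cut-off is more stable.* Over N=37 to 42 it stays at 6 while the one-sided cut-off moves at 41. But over N=29 to 40 the one-sided cut-off is 5 throughout and the equal-tail one moves at 34. N=42 cannot occur, because some Stage 1 and 2 patients had non-measurable disease and are excluded. The hypotheses are directional. The earlier PFS6 design (stop at 2 or fewer of 9, positive at 10 or more of 24) has upper-tail alpha 0.048 and power 0.805, so it was a one-sided 5% design.
- *Changing the primary endpoint after seeing responses leaves the pooled test without a needed caveat.* The change and its reason are stated openly in 4.3.6.1, 8.1, 8.3.1 and 8.4.1. Part of the rationale just before 4.3.5.1 is not in the text reviewed, so a missing caveat cannot be established.
- *The side would be chosen once the count is known.* Appendix 11.1 has observed responses discussed at monthly site meetings, but that is general oversight and not evidence of such an intention. It is only a reason to settle the choice early.

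**Conclusion.** The point holds as a should-fix matter of SAP wording. The named test is wrong for the primary endpoint, the powers and sample size are right for the one-sample exact binomial test, and the success criterion is undefined. The practical effect is confined to exactly 5 responders with 34 to 40 evaluable patients. If the true ORR is 5%, the chance of exactly 5 responders at N=37 is 2.6% (0.0359 − 0.0095 = 0.0264).

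This rests on reading the two-sided rule as equal-tail, which the stated 77% requires, and on an evaluable N near the planned 37. Either side is defensible. Two-sided is the conservative option, but the documents do not require it.

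**What to change.** 1. In 8.6.1 and 8.6.2.3, replace Fisher's exact test with the one-sample exact binomial test against 5% (ORR) and 20% (PFS6). Fisher's test in the biomarker association analyses of 8.6.3 is a separate use and is not affected.
2. In 8.6.1, report ORR with a Clopper-Pearson 95% interval.
3. In 8.4.1 and 8.6.1, adopt one alpha and side as governing before the final analysis. Date and justify the choice, and record that it was made after Stage 1 and 2 responses had been seen.
4. State the cut-off as a rule at the actual evaluable N, and quote only the matching power:
   - One-sided 5%: at least 5 of 37 (alpha 0.036, power 88.8%), rising to 6 from N=41.
   - Two-sided 5%, equal-tail and named as such: at least 6 of 37 (upper tail 0.0095, power 77.8%). The cut-off is 6 for N=34 to 42 (power 70.0% at N=34) and 5 for N=29 to 33.

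The cost is a few lines of SAP text, with no added patients, visits or data. Only one power figure remains quoted. Under the two-sided rule, 5 responders at N=34 to 40 no longer counts as success, but test and interval always agree. Under the one-sided rule, 5 of 37 is a success although its 95% interval includes 5%, and the plan should say so in advance.
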